## **7.8 Procedure(s) to account for missing or spurious data**

Participants will be encouraged to submit follow-up data via email/text reminders. Missing values will not be inputed, as completeness of data is a key feasibility outcome.

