# **7 STATISTICS AND DATA ANALYSIS**

The analysis of this trial will be mainly descriptive focusing on estimation rather than hypothesis testing. All baseline measures and outcomes will be summarised for each allocated group using the appropriate descriptive statistics and presented with their associated confidence intervals. No formal comparison of groups will take place. A Statistical Analysis Plan will be developed, setting out the details of all analyses and assumptions for the stage 3 pilot trial before the last patient is recruited.

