## **7.1 Sample size calculation**

Stage 3 represents a pilot trial so the effectiveness of the intervention is not being evaluated, therefore a formal power calculation is not appropriate. The sample size is based on a 95% confidence interval approach. For each of the expected proportions/means in the key objectives below, the precision to which we would be able to estimate the proportion/mean given this sample size is presented (nQuery and nTerim v4.0).

For the specific pilot trial objectives, the following are descriptions of the precision of our estimates with the stated assumptions:

i. *Recruitment rate*: It is estimated that the percentage of those approached who are randomised is around 30% therefore the approached sample size will be approximately 387 resulting in a half width for the confidence interval of 5%. The widest confidence interval for this approximation results when the percentage of randomised to approached is around 70% giving an approached sample size of 166 and a 95% confidence interval half width of 7%.

ii. *Acceptability and uptake of the intervention*: it is estimated that the uptake rate across those randomised to the intervention will be 90%, with 58 available participants for this estimation; this would result in a confidence interval half width of 8%.

iii. *Number of participants assessed at 6-months*: It is estimated that the dropout rate from the trial will be 20% of those randomised. With 116 participants randomised into the trial this would result in a confidence interval half width of 7% for the estimate of the dropout rate. Even when considering the statistical worst-case scenario of 50% the resulting confidence interval for this sample size has a half width of 9%.

iv. *Mean asthma related quality of life at 6 months in the control group*: with an estimated standard deviation of 1.4 from the UBIOPRED cohort (1), if data from 46 participants are available at 6 months and therefore

available for this estimation, this would give a confidence interval half width of 0.4 units approximately 0.3 standard deviations.

v. *Completeness of data for asthma related quality of life and healthcare utilisation data across the study in the two groups:* this is estimated at 95% across those randomised and still in the trial at 6 months, giving 92 participants available for this estimation therefore giving a confidence interval half width of 5%. Additionally, we plan to interview 10-20 participants in each intervention group.

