## 7.3 Primary outcome analysis

As this stage 3 protocol outlines a pilot stage for a definitive phase-3 trial, the primary outcomes will be related to feasibility. All patients will be analysed as randomised (intention-to-treat). Feasibility outcomes include:

- i. Assessing the recruitment rate by presenting the proportion of participants recruited among those approached;
- ii. Assessing the acceptability, uptake and use of the intervention, by presenting the proportion of intervention patients who use the intervention website, in conjunction with findings from qualitative data collection;
- iii. Estimating the follow-up rate at the 6-month assessment (additionally, looking at relative rates for participants recruited from primary care, secondary care, Asthma UK, social media, professional networks and snowballing);
- iv. To monitor the change in and estimate the variance of asthma-related quality of life and asthma control in each group;
- v. To determine if data collection methods for process, effectiveness and cost-effectiveness endpoints are appropriate for this population by assessment of completeness of data at 2 and 6-month assessments;
- vi. To determine whether the PedsQL Asthma Module (with and without the additional emotion questions) and the Paediatric Asthma Quality of Life Questionnaire provide similar information by estimating their pairwise correlation.
- vii. To assess the relative uptake and quality of qualitative data collection from participants via in-person, video or telephone interviews;

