## **7.7 Participant population**

The trial analysis will include all participants randomised into the trial, regardless of whether they received the intervention. In addition, an analysis will be undertaken on the protocol-compliant population who will be defined as those who have covered at least half of the training sessions in the online website.

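### Section 7.8 rules out imputation and the plan names no other method, so the 6-month mean, change and variance in 7.3(iv) rest only on participants with 6-month data

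*Combined protocol and SAP*

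**What the plan says.** The whole missing-data provision is in section 7.8. Participants are to be prompted ("Participants will be encouraged to submit follow-up data via email/text reminders"), and then: "Missing values will not be inputed, as completeness of data is a key feasibility outcome".

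Other parts of section 7 fix what analysis remains:

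- Section 7, opening paragraph: "The analysis of this trial will be mainly descriptive focusing on estimation rather than hypothesis testing", with summaries and confidence intervals by allocated group. "No formal comparison of groups will take place". A separate statistical analysis plan is to follow before the last patient is recruited.
- Section 7.3(iv) lists among the primary feasibility outcomes: "To monitor the change in and estimate the variance of asthma-related quality of life and asthma control in each group".
- Section 7.7: "The trial analysis will include all participants randomised into the trial, regardless of whether they received the intervention". Section 7.3 states the intention-to-treat principle.
- Section 7.6 (Adjusted analysis) plans no adjustment, and section 7.9 expects nothing further statistically.
- Section 7.1(iv) bases the precision of the control-group 6-month mean on observed data: "if data from 46 participants are available at 6 months".

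Quality of life and asthma control are collected at baseline, 2 months and 6 months (section 5.1; Appendix 1). No repeated-measures method, missing-data sensitivity analysis or comparison of those lost with those retained is described.

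**The concern.** The rule and its reason do not match. Completeness (7.3(v)) is counted from the raw data whatever is done with the scores, so making it an outcome is a reason to report it. It is not a reason to leave out baseline and 2-month scores, already collected, when estimating the 6-month quantities in 7.3(iv).

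Informative loss is plausible here. The trial is open (5.5.5), controls wait for access until the end (5.2, 5.5.4), and follow-up is by email link with two reminders (5.5.8). Participants who have seen little change by 2 months may be less likely to answer at 6 months, and not necessarily equally in the two arms. The 6-month change and SD are what the planners of the definitive trial will read. If completers differ from those lost, the estimate shifts and its confidence interval does not show it.

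**Working it through.** **1. The plan's own figure.** Inputs from 7.1 and 7.2: 58 per arm, 20% dropout, SD 1.4, 95% interval.

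- Available per arm: 58 × 0.8 = 46.4, stated as 46. Both arms: 116 × 0.8 = 92.8, stated as 92.
- Half width: 1.96 × 1.4 / √46 = 0.405 units, or 1.96 / √46 = 0.289 SD. The plan's 0.4 units and roughly 0.3 SD reproduce.

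The figure is therefore a completer figure: 58 − 46 = 12 controls do not contribute. If all 58 were fully informative (an upper bound), the half width would be 1.96 × 1.4 / √58 = 0.360.

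**2. Size of a completer shift.** For any mean, including mean change:

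completer mean − full mean = d × (completer mean − mean of those lost), where d is the proportion lost.

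At d = 0.20, assumed gaps of 0.25, 0.50 and 0.75 SD give 0.05, 0.10 and 0.15 SD. The documents give no gap, so these are a range and not a prediction. SD units are used because it is unclear that the SD of 1.4 is on the same scale as the eligibility cut-off of 85 in section 5.4.

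**3. Loss that depends on early change (assumed).** Scores are trivariate normal with unit SD and correlations 0.6 (0-2 months), 0.5 (0-6) and 0.7 (2-6). Overall loss is 20%. The log-odds of loss rise by 0.5, 1.0 or 1.5 per SD less improvement by month 2, which are odds ratios of about 1.6, 2.7 and 4.5. The covariance between 0-2 and 0-6 month change is 0.7 − 0.6 − 0.5 + 1 = 0.6, so selecting on early change also selects on 6-month change.

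| Log-odds slope | Completer bias in 6-month change (SD) | Implied gap, bias / 0.20 (SD) |
|---|---|---|
| 0.5 | 0.064 | 0.32 |
| 1.0 | 0.115 | 0.575 |
| 1.5 | 0.150 | 0.75 |

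The assumed SD of 0-6 month change is √(1 + 1 − 2 × 0.5) = 1 score SD, so the half width for mean change is also about 0.289 SD. The bias is 0.064 / 0.289 = 22% to 0.150 / 0.289 = 52% of it. The completer SD of change is about 1-4% too small.

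**4. Using all available scores in the same setting.** If everyone lost gave a 2-month score, the bias is 0.002 SD or less. If half did not, about 0.02-0.04 SD remains. If none did, about 0.04-0.10 SD remains.

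**5. Loss that depends on the 2-month level (assumed).** With equal correlations of 0.5 or 0.7 and log-odds rising 0.5 or 1.0 per SD worse 2-month score, the completer 6-month mean is off by 0.05-0.12 SD and its SD is 0.6-2.8% too small. Bias in change is essentially nil, because the covariance of 6-month change with the 2-month score is ρ − ρ = 0.

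**6. SD bias against sampling error.** The 95% interval for an SD of 1.4 at n = 46 is 1.16 to 1.76, that is 1.16 / 1.4 = 0.83 to 1.76 / 1.4 = 1.26 times the value. A bias of 1-4% is small beside that.

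**The case against.** The strongest reply is that this is a pilot with descriptive aims, no group comparison and a detailed analysis plan still to come, and that 7.1 openly states the reduced number. Much of that stands. It limits the consequences and leaves room for the fix. It does not supply a method, and 7.6 and 7.9 point to none being intended.

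Several stronger readings are tempting, and the documents do not support them:

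- *That the plan bars any handling of missing data.* Section 7.8 bars imputation only. A likelihood model on observed scores imputes nothing and is not prohibited. It is simply not specified.
- *That earlier scores of those lost are discarded.* All outcomes are to be summarised by group, so those scores appear in the baseline and 2-month summaries. They are unused only for the 6-month estimates.
- *That 7.8 contradicts intention-to-treat.* Sections 7.3 and 7.7 define who belongs to which group, in contrast to the protocol-compliant set. They do not promise a 6-month value for everyone.
- *That completer change is overstated.* It may be. The correlations and the loss mechanism are assumptions, and step 5 gives a pattern with no bias in change.
- *That a repeated-measures model removes the bias.* It does so only under missing-at-random with 2-month scores available.
- *That the bias should be set against the adult effect of 0.28 (section 1.3).* That is a between-group difference. A bias within one arm is a different quantity, similar bias in both arms would cancel in a difference, and differential loss has not been modelled here.

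**Conclusion.** The point holds in a limited form. As written, the plan yields observed-case 6-month means, changes and variances from about 46 of 58 per arm, and the reason in 7.8 does not justify stopping there for 7.3(iv). Under loss driven by early change, completer change may be too favourable by about 0.06-0.15 SD, up to about half of the planned half width. Under another reasonable pattern the bias in change is near nil, though the 6-month mean still shifts by 0.05-0.12 SD. The case rests on the mean and the mean change, since bias in the SD is minor beside its sampling error. All the bias figures depend on assumed correlations and loss mechanisms and on the plan's 20% dropout. This is an inexpensive improvement to the analysis and does not undermine the pilot.

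**What to change.** In 7.8 and the forthcoming statistical analysis plan:

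1. Keep raw, unimputed counts for the completeness outcome, 7.3(v).
2. Label 6-month summaries as observed-case and give the denominator for each arm.
3. Tabulate baseline and 2-month scores by 6-month status (data present or absent) and arm.
4. Beside the observed-case result for 7.3(iv), report per-arm 2- and 6-month mean, change and SD from a likelihood-based repeated-measures model (arm by visit, unstructured covariance) on all available baseline, 2- and 6-month scores, labelled as supportive. Estimate the covariance separately by arm so that the SDs are arm-specific. With three visits that is 3 variances and 3 covariances per arm.
5. State that the model assumes missing-at-random, and report how many of those lost at 6 months have a 2-month score.

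The cost is some wording, one table and one standard model per outcome. No new data, participants or group comparison are needed. The downside is the missing-at-random assumption: in the setting of step 3, about 0.02-0.04 SD of bias remains if half of those lost lack a 2-month score, and bias also remains if loss depends on unobserved 6-month scores. The observed-case result should therefore stay alongside.

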## **7.9 Other statistical considerations.**

There are no further anticipated statistical considerations. All deviations from the Statistical Analysis Plan will be recorded.

# **8 DATA MANAGEMENT**

## **8.1 Data collection tools and source document identification**

Source data will be recorded on the trial website. This will downloaded into one of two CSV files:

- (a) Personal data file – this will include names and contact information that is required to conduct the trial. This will be kept within the University Southampton NHS Foundation Trust IT environment.
- (b) Trial data file – this will include trial data but no personal data (exception will be ethnicity coded as white/non-white and date of birth which will be coded as month/year). This will be read into statistical software (e.g. STATA, SPSS).

The exceptions will be:

- the paediatric asthma quality of life questionnaire which will be collected on paper (source document). These data will be entered into SPSS and double checked. Data will then be transferred to statistical software (e.g. STATA, SPSS).
- Transcripts of interviews which will be kept as word document (source document) and any recordings destroyed to maintain confidentiality.

## **8.2 Data handling and record keeping**

Participants will be labelled with a unique identification number assigned by the trial website.

Copies for source data will be kept.

Source data from the trial website and paediatric asthma quality of life questionnaires will be merged to form the trial database in statistical software (e.g. STATA, SPSS). Data will be cleaned with identification of values outside set ranges and unlikely give other data; these will be corrected where possible in the trial analysis data set. A list of any edits will be kept.

### **8.3 Access to Data**

Direct access will be granted to authorised representatives from the Sponsor, host institution and the regulatory authorities to permit trial-related monitoring, audits and inspections- in line with participant consent.

### **8.4 Archiving**

The source data and trial analysis data set with explanatory documentation will be achieved at the end of the trial. For this, the trial questionnaires will be scanned.

Documents with confidential information will be archived by University Hospital Southampton NHS Foundation Trust. All other documents will be archived by the University of Southampton. All data will be kept for a minimum of 10 years after the completion of the trial.

## **9 MONITORING, AUDIT & INSPECTION**

The Trial Monitoring Plan is:

- Study team will monitor all trial informed consent documentation, trial data and transcripts to ensure that study conduct is as per the protocol. Additionally, the team will undertake a face to face or virtual review of activity at each site after the first participant is recruited.
- Trial management group will monitor recruitment, trial data (whole trial, not grouped) and serious adverse events at least 2 monthly.
- Trial Steering Group will review recruitment, trial data (whole trial, not grouped) and serious adverse events at 6 monthly.

It is expected that the Sponsor may also choose to monitor the study.

## 10 ETHICAL AND REGULATORY CONSIDERATIONS

### 10.1 Assessment and management of risk

The study team have evaluated the risks associated with the trial and classified it as low risk.

| Risk   | Level    | Mitigation  |
|--|----------|---|
| Participant's asthma deteriorates over the course of the study and this is not adequately managed.             | Low      | It is likely that some participant's asthma control will deteriorate over the 6-month trial as this is the natural course of asthma and half of the participants will be in the control group. The trial website informs participants and their parents that they should contact their asthma doctor if they have increasing symptoms that are not controlled by their medication. Where a participant contacts the study team with worrying symptoms, one of the trial doctors will be involved and appropriate advice given to keep the participant safe. |
| Participant reveals concerning information during an interview, for example they are having suicidal ideation. | Very low | In our experience, this is very unlikely. If this was to occur, the study team will initially talk to the participant's parent or guardian and, if necessary, their doctor to ensure they are kept safe.  |
| Data breach from the trial website   | Very low | There is a need for the trial website to collect some personal data to conduct the trial, for example contact details for participants and parents. This is a very small risk of a data breach from the trial website. This will be minimised by the use of use https, SSL certificates and JWT secure tokens. Personal data will not be downloaded with trial data. Where it is downloaded to enable the conduct of the trial, it will be held on a secure NHS sever.  |

### 10.2 Research Ethics Committee (REC) review & reports

Before the start of the trial, approval will be sought from a REC for the trial protocol, informed consent forms and other relevant documents. Substantial amendments that require review by REC will not be implemented until the REC grants a favourable opinion for the trial. All correspondence with the REC will be retained in the Trial Master File/Investigator Site File. The Chief Investigator will submit an annual progress report (APR) to the REC within 30 days of the anniversary date on which the favourable opinion was given, and annually until the trial is declared ended. The Chief Investigator will notify the REC of the end of the Study. Within one year after the end of the trial, the Chief Investigator will submit a final report with the results, including any publications/abstracts, to the REC.

### 10.3 Peer review

The NIHR RfPB panel has peer reviewed this study.

### 10.4 Public and Patient Involvement

We have and will involve young people and their parents in:

- Interpreting the findings of stage 1 and 2
- designing the pilot trial
- interpreting the findings of stage 3
- reporting and dissemination

We plan to achieve this with:

- Two local Patient and Public Involvement (PPI) panels: 7 young people and 7 parents – quarterly meetings, in parallel, outside school hours, facilitated by study personnel, with feedback from project and TSC – panels will receive training.
- Asthma UK – are involved in the management of the trial
- PPI representation on the Trial Steering Committee – We would support one member of each of the local young person and parent PPI panels to represent the panels' views on the trial steering committee.

## **10.5 Protocol compliance**

Any protocol deviations will be documented in the site investigator's file. Any serious will be immediately reported to the Chief Investigator and Sponsor. A "serious breach" is a breach which is likely to effect to a significant degree: (a) the safety or physical or mental integrity of the participants of the trial; or (b) the scientific value of the trial.

## **10.6 Data protection and patient confidentiality**

All investigators and trial site staff will comply with the requirements of the General Data Protection Regulations 2018 with regards to the collection, storage, processing and disclosure of personal information and will uphold the Act's core principles.

Personal information will be kept secure in the site investigator file. Each participant will have a numerical identifier which will be used to label the participant's CRF and transcripts.

Prior to analysis, the data will be anonymised by destroying the file linking personal details with the participants' identifiers.

Data will be stored for 10 years. [name] is the data custodian.

## **10.7 Financial and other competing interests for the chief investigator, PIs at each site and committee members for the overall trial management**

None of the investigator have any commercial interests. They are though in receipt of funding from the NIHR RfPB to undertake the study. Also one of the investigators works for Asthma UK which is a charity that aims improve the life of people with asthma. A list of conflicts of interest will be reviewed at each TSC meeting and updated as needed.

## **10.8 Indemnity**

The sponsor of the project is University Hospital Southampton NHS Foundation Trust. For NHS sponsored research HSG (96) 48 reference no.2 refers. If there is negligent harm during the clinical project when the NHS body owes a duty of care to the person harmed, NHS Indemnity covers NHS staff, medical academic staff with honorary contracts, and those conducting the project. NHS Indemnity does not offer no-fault compensation and is unable to agree in advance to pay compensation for non-negligent harm. Ex-gratia payments may be considered in the case of a claim.

## **10.9 Amendments**

Any amendments will be made by the TMG. The Sponsor will decide whether an amendment is substantial or non-substantial. They will be notified to the UHS R&D office (as the lead organisation) and communicated to other participating organisations so participating sites to assess whether the amendment affects the NHS permission for that site.

## **10.12 Access to the final trial dataset**

All the trial investigators will have access to the anonymised study dataset.

## **11 DISSEMINATION POLICY**

### **11.1 Dissemination policy**

The study data will be owned by the University of Southampton. At the end of the trial, the investigators will analyse the data and generate a final trial report. The intention is that it will be published in a peer reviewed journal acknowledging the funder. It may also be presented at meeting. Additionally, a summary of the study findings will be provided to the study participants.

